5.6.2 Confidence interval for relative reduction

5.6.2.1 Annualized rate of change in TKV

The relative reduction in annualized rate of change in TKV for venglustat 15 mg dose versus placebo is defined as:

$$RR_{15} = \left(1 - \frac{\widehat{\theta_{15}}}{\widehat{\theta_0}}\right) \times 100$$

where:

$$\widehat{ heta}_{\iota}=$$
 Annualized rate of change in TKV in arm i $=10^{\widehat{eta}_{\iota}}-1$

and $\widehat{\beta}_t$ is the slope of log₁₀-transformed TKV in arm i (i=0 for the placebo arm and i=15 for the venglustat 15 mg dose arm), estimated from the linear mixed-effect model.

Using the properties of the log-normal distribution in base 10, it can be shown that $\widehat{\theta}_i$ has mean and variance equal to m_i and s_i^2 :

$$m_i = \exp\left(\widehat{\beta}_i \ln 10 + \frac{Var(\widehat{\beta}_i)(\ln 10)^2}{2}\right) - 1$$

$$s_i^2 = \exp[2\widehat{\beta}_i \ln 10 + Var(\widehat{\beta}_i)(\ln 10)^2](\exp[Var(\widehat{\beta}_i)(\ln 10)^2] - 1)$$

Using the Fieller method, the $100 \times (1 - \alpha)\%$ confidence interval of the ratio $\frac{\widehat{\theta_{15}}}{\widehat{\theta_0}}$ has lower and upper limit equal to L_{15} and U_{15} :

$$L_{15} = \frac{m_0 m_{15} - \sqrt{(m_0 m_{15})^2 - \left(m_0^2 - {z_{\alpha/2}}^2 s_0^2\right) \left(m_{15}^2 - {z_{\alpha/2}}^2 s_{15}^2\right)}}{m_0^2 - {z_{\alpha/2}}^2 s_0^2}$$

$$U_{15} = \frac{m_0 m_{15} + \sqrt{(m_0 m_{15})^2 - \left(m_0^2 - z_{\alpha/2}^2 s_0^2\right) \left(m_{15}^2 - z_{\alpha/2}^2 s_{15}^2\right)}}{m_0^2 - z_{\alpha/2}^2 s_0^2}$$

where $z_{\alpha/2}$ is the quantile of the normal distribution.

Therefore, the 95% confidence interval for the relative reduction in annualized rate of change in TKV for venglustat 15mg dose versus placebo will be calculated as:

$$(1-U_{15}) \times 100$$
; $(1-L_{15}) \times 100$

The same method will be used for the relative reduction of venglustat 8 mg dose versus placebo.

5.6.2.2 Annualized rate of change in eGFR

The same method will be used for the relative reduction in annualized rate of change in eGFR, with the exception that in absence of log_{10} -transformation, RR_{15} , m_i and s_i^2 are defined as:

$$RR_{15} = \left(1 - \frac{\widehat{\beta_{15}}}{\widehat{\beta_0}}\right) \times 100$$

$$m_i = \widehat{\beta_i}$$

$$s_i^2 = Var(\widehat{\beta_i})$$

where $\widehat{\beta}_{i}$ is the slope of eGFR in arm i, estimated from the linear mixed-effect model.

5.6.3 P-values from multiple comparison procedure

As described in Section 4.3.1.2, the overall effect of venglustat will be assessed using 3 prespecified contrasts Z_1 , Z_2 and Z_3 . (corresponding to the contrasts associated with the candidate models Emax, linear and Sigmoid Emax). The test statistic Z is the maximum of Z_1 , Z_2 and Z_3 .

Assuming the observed statistic is Z_{obs} , the one-sided p-value from the Multiple Comparison Procedure can be defined as the probability that Z is greater than Z_{obs} , under the null hypothesis. In the asymptotic case, random samples of Z under the null hypothesis can be generated using the SAS code below.

The two-sided p-value will be defined as twice the one-sided p-value, and truncated to 1 in case the one-sided p-value is greater than 0.5.

```
* Observed Z statistic;
%let Zobs = 2.25;
data pvalue;
  * Initialization of seed ;
  retain seed 15392;
  * Initialize the number of samples with Z > Zobs;
  Ngreater = 0;
  * Generate 1000000 samples from the distribution of the Z statistic
under the null hypothesis;
  do i=1 to 1000000;
    * Generate independent normal for the 3 arms;
    call rannor(seed,u0);
    call rannor(seed, u1);
    call rannor (seed, u2);
    * Calculate the 3 contrasts ;
    Z1 = -0.8131*u0 + 0.3424*u1 + 0.4707*u2;
    Z2 = -0.7223*u0 + 0.0314*u1 + 0.6909*u2;
    Z3 = -0.6615*u0 - 0.0838*u1 + 0.7453*u2;
    * Z-statistic : maximum of all contrasts ;
    Z = Max(Z1, Z2, Z3);
    * Increment the number of samples with Z > Zobs;
    Ngreater = Ngreater + (Z > &Zobs);
  end;
  * One-sided pvalue ;
  pvalue onesided = Ngreater/1000000;
  * Two-sided p-value ;
  pvalue twosided = min(2*pvalue onesided,1);
run;
```

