Primary endpoint (treatment policy)	Annualized rate of change in eGFR (CKD-EPI equation) from baseline to 24 months	Combined Stage 1 and Stage 2 ITT	regardless of adherence to study intervention	Analysis of eGFR in Stage 2 will be identical to the one of Stage 1	

Endpoint			Estimands	
Category (estimand)	Endpoint	Population	Intercurrent event(s) handling strategy	Population-level summary (Analysis and missing data handling)
Secondary objectives	: To determine the effect of vengl To determine the effect of vengle		KV growth gue, based on patient reported diary	
Secondary endpoint (treatment policy)	Annualized rate of change in TKV based on MRI from baseline to 18 months	Combined Stage 1 and Stage 2 ITT	regardless of adherence to study intervention	Analysis not done as no post-baseline MRI data available on Stage 2 at the time of study discontinuation
Secondary endpoint (treatment policy)	Change in pain (BPI Item 3) from baseline to 24 months	Combined Stage 1 and Stage 2 ITT	regardless of adherence to study intervention	Analysis of pain in Stage 2 will be identical to the one of Stage 1
Secondary endpoint (treatment policy)	Change in fatigue (BFI Item 3) from baseline to 24 months	Combined Stage 1 and Stage 2 ITT	regardless of adherence to study intervention	Analysis of fatigue in Stage 2 will be identical to the one of Stage 1

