2 SAMPLE SIZE DETERMINATION

In Stage 1, approximately 240 participants will be randomized (with randomization ratio 1:1:1) to placebo (n=80) or venglustat 8 mg (n=80) or venglustat 15 mg (n=80mg).

In Stage 2, approximately 320 participants with an eGFR between 45 and 89.9 mL/min/1.73 m² at screening will be randomized (with randomization ratio 1:1) to placebo (n=160) or venglustat (n=160).

In addition, 80 participants with an eGFR between 30 and 44.9 mL/min/1.73 m² at screening will be randomized (with randomization ratio 1:1) to placebo (n=40) or venglustat (n=40). The participants from Stage 2 with an eGFR between 30 and 44.9 mL/min/1.73 m² will not be included in the primary efficacy and safety analyses populations but the data from these participants will be analyzed separately.

This sample size will provide approximately 89% power to detect a 50% reduction in annualized rate of change in TKV at end of Stage 1 and approximately 87% power to detect a 30% reduction in annualized rate of change in eGFR between venglustat and placebo at the end of Stage 2. Overall, the total sample size will provide approximately 87% power to detect an effect on both TKV and eGFR.

Sample size and power calculations were based on simulations, assuming different scenarios regarding the dose-response relationship (Section 5.6.1). SAS program is provided in (Section 5.5). The following model parameters were estimated based on available datasets from a similar participant population (participants aged 18 to 50 years with Mayo class 1C-1E and baseline eGFR from 45 to 90 mL/min/1.73 m²) in 2 historical studies (Consortium for Radiologic Imaging Studies of Polycystic Kidney Disease (CRISP) and the Polycystic Kidney Disease Treatment Network ([HALT-PKD]):

- A slope of log10(TKV) of 0.02591, 0.02832 and 0.03141 in participants from Mayo class 1C, 1D and 1E respectively (corresponding to 6.1%, 6.7% and 7.5% increase per year in TKV), resulting in average slope of 0.02764 (6.6%/year) assuming 50% of 1C, 33% of 1D and 17% of 1E.
- Standard deviation for the residual error of TKV (on the log10 scale) of 0.02566 and standard deviation for the random effect of slope of 0.01477.
- A slope of eGFR of -3.16, -3.88 and -4.69 mL/min/1.73 m² per year in participants from Mayo class 1C, 1D and 1E respectively, resulting in average slope of -3.66 mL/min/1.73 m² per year assuming 50% of 1C, 33% of 1D and 17% of 1E.

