4.3.1.2 Main analytical approach

A linear mixed effect model will be fitted to the log10-transformed TKV, which will include fix effects of treatment (venglustat 15 mg, venglustat 8 mg or placebo), Mayo Imaging Classification (as per randomization stratification factor: class 1C versus 1D versus 1E), time (as continuous variable), treatment * time interaction and Mayo Imaging Classification * time interaction, and will include random intercept and slope. Time will be based on actual TKV assessment date relative to randomization date (in years).

Within group mean slope of log10-transformed TKV will be obtained from the linear mixed effect model, using weights for each stratum (Mayo class 1C, 1D and 1E) equal to the overall proportion of participants in each stratum in the Stage 1 ITT population (ie, "population weight"). A backtransformation will be applied to obtain annualized rate of change in TKV (in % per year) within each treatment arm, along with their 95% confidence intervals (CI).

Overall effect of venglustat will be assessed using a Multiple Comparison Procedure. Multiple trend tests will be performed using optimal contrasts determined from a set of 3 prespecified candidate models for the dose-response relationship described in Figure 1.

[figure not shown]

Figure 1 - Prespecified candidate of dose-response models

Optimal contrasts for each candidate model were derived using the R add-on package DoseFinding (2, 3) and are presented in Table 5. Contrasts will apply to treatment * time interaction term in the linear mixed effect model. P-value from the Multiple Comparison Procedure will be calculated as described in Section 5.6.3.

Linear model Dose E_{max} model Sigmoid E_{max} model Placebo -0.8131 -0.7223-0.6615GZ/SAR402671 8 mg 0.3424 0.0314 -0.0838 GZ/SAR402671 15 mg 0.4707 0.6909 0.7453

Table 5 - Optimal contrasts for the 3 prespecified candidate of dose-response models

Relative reduction in annualized rate of change in TKV will be estimated for each dose of venglustat versus placebo and defined as:

Relative reduction (%) =
$$\left(1 - \frac{\text{Annualized rate of change in TKV in GZ/SAR4026 71 arm}}{\text{Annualized rate of change in TKV in placebo arm}}\right) \times 100$$

Relative reduction for each dose of venglustat will be presented with 95% confidence intervals obtained using Fieller method (see Section 5.6.2) only if significant change is observed in the

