4.3.2.2 Main analytical approach

The analysis of eGFR will be similar to those of TKV, with the exception that no log transformation will be used for eGFR (see Section 4.3.1.2).

Primary analysis in Stage 2 will combine all data from Stage 1 and Stage 2 available from baseline to the end of the 24-month double-blind core treatment period. Primary analysis will include all observed eGFR data in randomized participants, regardless of whether or not participants completed the treatment period (treatment policy strategy). Participants who prematurely and permanently discontinue study medication will be requested to obtain eGFR at 24 months.

No imputation of missing data will be performed.

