4.4.1.2 Main analytical approach

The analysis of eGFR in Stage 1 will be identical to those of Stage 2 (see Section 4.3.2.2).

Daily diaries scores will be averaged over 7 consecutive assessments prior to the baseline, Month 3 and Month 12 visit and over the 14 consecutive days prior to the planned Month 18 visit. At least 50% of the days in the observation period (ie, 4 or more of the 7 days for baseline, Month 3 and Month 12; 7 or more of the 14 days for Month 18) are required to calculate the average score on non-missing data (4, 5).

Change in pain and change in fatigue from baseline to 18 months will be analyzed on the ITT population, regardless of whether or not participants completed the treatment period, using a mixed effect model with repeated measures (MMRM). The model will include the fixed categorical effects of treatment (venglustat 15 mg, venglustat 8 mg or placebo), Mayo Imaging Classification (as per randomization stratification factor: Class 1C versus 1D versus 1E), time point (Month 3, Month 12, Month 18), treatment-by-time point interaction, randomization strataby-time point interaction as well as the continuous fixed covariates of baseline and the baseline-by-time point interaction.

This model will be run using SAS Mixed procedure with an unstructured correlation matrix to model the within-patient errors. Parameters will be estimated using restricted maximum likelihood method. Denominator degrees of freedom will be estimated using Kenward-Roger approximation. This model will provide baseline adjusted least-squares means estimates at Month 18 for each study intervention groups with their corresponding standard errors (SEs) and 95% confidence intervals (CI). Within group mean change in pain will be obtained from the MMRM, using weights for each stratum (Mayo Class 1C, 1D and 1E) equal to the overall proportion of participants in each stratum in the Stage 1 ITT population (ie, "population weight"). Population weights are considered more appropriate than equal coefficients due to expected unbalances in the study population between levels of the randomization stratification factors.

Overall effect of venglustat will be assessed using a Multiple Comparison Procedure similar to those of the primary endpoint (see Section 4.3.1.2). In addition, p values for the comparison of each dose of venglustat versus placebo will be presented for descriptive purpose.

There will be no imputation of missing data.

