4.9 INTERIM ANALYSES

4.9.1 Dose selection safety review

The dose selection safety review was performed when the first 150 participants from Stage 1 have completed 1 month of treatment (or have prematurely discontinued).

The dose selection safety review was performed by the DMC. An unblinded safety report was prepared by the external independent DMC statistician and was reviewed by the DMC. Safety data included AEs (including SAEs and AEs leading to permanent intervention discontinuation), clinical laboratory evaluation, ECG, physical and ophthalmological examination, and BDI-II data.

Based on this safety review, the DMC selected the venglustat 15mg dose for Stage 2. The venglustat 15 mg dose was the highest dose determined to be safe and well tolerated.

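### The SAP's null distribution for the max-contrast test assumes equally precise arms, so the combined eGFR primary p-value comes out too small

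*SAP*

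**What the plan says.** SAP 5.6.3 takes the maximum of three contrast statistics (Emax, linear, sigmoid Emax) and defines the one-sided p-value, correctly, as the probability under the null that this maximum exceeds the observed value. The only means it supplies is SAS code with the step "Generate independent normal for the 3 arms". Three standard normals are drawn and the Table 5 coefficients are applied to them without rescaling. "The two-sided p-value will be defined as twice the one-sided p-value".

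The recipe is not limited to Stage 1:

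- SAP 4.3.1.2: "P-value from the Multiple Comparison Procedure will be calculated as described in Section 5.6.3".
- SAP Table 3 (1.2.1): "Analysis of eGFR in Stage 2 will be identical to the one of Stage 1".
- SAP 4.3.2.2 is slightly looser: "The analysis of eGFR will be similar to those of TKV".
- SAP 4.4.1.2, for pain and fatigue: "Overall effect of venglustat will be assessed using a Multiple Comparison Procedure similar to those of the primary endpoint".

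No other null is given anywhere. The power program in SAP 5.5 builds the same equal-variance null in its Step 3 and applies it to the end-of-Stage-2 eGFR test.

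On allocation, Stage 1 randomises 80 per arm. Stage 2 adds 160 placebo and 160 venglustat patients in the main eGFR range (SAP 2), and SAP 4.9.1 records that "the DMC selected the venglustat 15mg dose for Stage 2".

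**The concern.** Independent unit-variance draws represent the null only if the three arm slopes are estimated with equal precision. In the combined analysis the 8 mg arm stays at 80 while the other two grow to 240. Each observed contrast is divided by its own model standard error, so each statistic is still about N(0,1). The correlations between the three change, however, and the tail of a maximum depends on those correlations. Lower correlation means a larger maximum under the null, so the code's p-value is too small.

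This is the p-value rule for the Stage 2 primary endpoint, and SAP 4.6 promises strong type I error control on the strength of it. The test rejects only for benefit, so a literal 5% rejection rate is not breached. What is exceeded at the planned allocation is the one-sided 0.025 implied by a two-sided 0.05.

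**Working it through.** **Inputs.** Contrasts (placebo, 8 mg, 15 mg) from SAP Table 5: Emax (-0.8131, 0.3424, 0.4707); linear (-0.7223, 0.0314, 0.6909); sigmoid Emax (-0.6615, -0.0838, 0.7453). Each sums to 0 and has length 1 to rounding. Levels for the combined eGFR test from SAP Figure 2: 0.01 if TKV fails at Stage 1, and 0.01 + 0.975 × 0.04 = 0.049 if it succeeds. One-sided these are 0.005 and 0.0245.

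**The plan's own figures first.** A patient-level simulation (3,000 trials per scenario) used the SAP's design, variances, dropout, futility rule and alpha rules, with critical values from the SAP's equal-variance null. It gave eGFR power of 89.2% in scenario 1 (stated 90.1%), 86.2% in scenario 2 (87.0%) and 80.4% in scenario 7 (80.1%). TKV power was 92.2% and 88.6% in scenarios 1 and 2 (stated 92.6% and 89.0%). The procedure is therefore read as intended.

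**Correlations.** With D = diag(variances of the arm slopes), corr(Zi, Zj) = ci'Dcj / sqrt(ci'Dci × cj'Dcj). At 240:80:240, D is proportional to diag(1, 3, 1). For Emax and linear:

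- numerator: 0.8131×0.7223 + 3×0.3424×0.0314 + 0.4707×0.6909 = 0.9448
- Emax variance: 0.8131² + 3×0.3424² + 0.4707² = 1.2344
- linear variance: 0.7223² + 3×0.0314² + 0.6909² = 1.0020
- correlation: 0.9448 / sqrt(1.2344 × 1.0020) = 0.849

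| Pair | Equal arms (SAP code) | 240:80:240 |
|---|---|---|
| Emax, linear | 0.923 | 0.849 |
| Emax, sigmoid | 0.860 | 0.717 |
| linear, sigmoid | 0.990 | 0.977 |

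**Tail of the maximum.** The contrasts sum to zero, so they span two dimensions and the tail is exact: P(max > x) = (1/2π) ∫ exp(-x² / 2m(θ)²) dθ over angles with m(θ) > 0, where m(θ) is the largest standardised contrast in direction θ. The SAP null gives critical Z = 2.142 at 0.0245. At 240:80:240 it should be 2.197.

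The ratio below is slope information in placebo or 15 mg relative to 8 mg.

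| Ratio | True error at 0.0245 (doubled) | True error at 0.005 (doubled) | p at Z = 2.25 |
|---|---|---|---|
| 1 (Stage 1) | 0.0245 (0.0490) | 0.0050 (0.0100) | 0.0188 |
| 1.03 | 0.0246 (0.0491) | 0.0050 (0.0100) | 0.0189 |
| 1.79 | 0.0261 (0.0523) | 0.0054 (0.0107) | 0.0201 |
| 2.05 | 0.0266 (0.0531) | 0.0055 (0.0109) | 0.0205 |
| 3 (240:80:240) | 0.0279 (0.0559) | 0.0057 (0.0115) | 0.0215 |

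At ratio 3 the true p is 0.0215 / 0.0188 = 1.14 times the code's value.

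**Both eGFR tests together.** With TKV effective and eGFR null, eGFR is tested at 0.025 × 0.04 = 0.001 at Stage 1 and at 0.049 at Stage 2 (doubled scale). Assuming Stage 1 eGFR information of 0.75 at the cut-off, ten million draws give a one-sided error of 0.0283 with the SAP null and 0.0247 with the correct one.

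**The truncated analysis.** SAP version 2 analyses whatever is available at database lock. Stage 2 enrolment and follow-up are not stated. SAP 4.4.2.2 reports no post-baseline Stage 2 MRI, and Protocol 9.4.1 schedules the only one at Month 18, which indicates that no Stage 2 patient had reached Month 18. The ratio was computed as GLS slope information with the documents' variances (random intercept 106.81, slope 3.90, covariance 5.36, residual SD 6.34). Assumed patterns were 40 to 160 Stage 2 patients per arm, follow-up spread over Months 1-9 or 1-15, and Stage 1 follow-up from the interim pattern up to Month 24. The ratio runs from 1.03 to 1.79. Holding Stage 1 at the interim minimum (70% at Month 9, 30% at Month 18) with 160 per arm spread over Months 1-15 gives 2.05.

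**The replacement.** Ten million draws from N(0, S), judged at the SAP's 0.0245 cut-off, gave 0.0245, 0.0260 and 0.0280 at ratios 1, 1.79 and 3, against exact values of 0.0245, 0.0261 and 0.0279.

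**The case against.** The strongest reply is that 240:80:240 with full follow-up will never be analysed. SAP version 2 postdates the futility decision and calls for one analysis of the data in hand, so the larger numbers are counterfactual. What remains is a shift in the third or fourth decimal place, and its size rests on assumed Stage 2 follow-up. That stands, and it is why the point is minor. If all 160 per arm had reached Month 15 the ratio would be 1.8 to 4.0. Staggered recruitment makes that implausible, but the documents do not exclude it.

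Section 5.6.3 also defines the p-value correctly and offers the code as one way to generate the null, so a careful programmer could use the right covariance. This does not rescue the text: SAP 5.5 applies the equal-variance null to the Stage 2 eGFR test, which shows the intended use.

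The error quoted for the two eGFR tests is the unfavourable configuration. With no effect on either endpoint, the one-sided error over TKV at 0.02 and eGFR at 0.005 by the recipe is about 0.0255 at the planned allocation. That is fair, but strong control has to hold in the unfavourable case too.

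The consequence for combined pain and fatigue is weak. In Figure 2, as far as it can be read, they sit below combined TKV, which will not be analysed, and SAP 4.4.2.2 falls back to descriptive summaries if the MMRM does not converge. If the tests are run, assumed visit correlations of 0.3 to 0.8 and assumed visit counts give ratios of 1.03 to 1.57 and an error of 0.0246 to 0.0257 at nominal 0.0245.

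**Conclusion.** The p-value rule is wrong as written for the combined eGFR primary analysis and right for Stage 1. At the planned allocation it understates the p-value by enough to raise the error by about 14-15% relative to nominal. This needs only the Table 5 contrasts and the planned sizes, with slope information proportional to arm size.

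In the analysis that will actually be run, the error is about 0.0246 to 0.0261 at nominal 0.0245 and 0.0050 to 0.0054 at nominal 0.005. The p-value at Z = 2.25 would be 0.3% to 7% larger. These ranges rest on the assumed enrolment and follow-up above. The 0.005 level (0.01 doubled) is the likelier one to apply after a futility stop on TKV.

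The direction follows from the dose selected. Had 8 mg gone forward (240:240:80), the recipe would have been slightly conservative, at 0.0468 against 0.049. Severity is minor; confidence is high for the mechanism and the planned-allocation figures, lower for the exact size in the truncated data.

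**What to change.** Keep the Table 5 contrasts and replace the three unit-variance draws in SAP 5.6.3 with text to this effect:

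> For each analysis, let S be the model-estimated 3×3 covariance matrix of the arm slopes (for the MMRM, of the arm means at the analysis time point). Draw u from N(0, S). For each Table 5 contrast c, compute c'u / sqrt(c'Sc). The one-sided p-value is the proportion of draws in which the largest of the three exceeds the observed Z.

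With equally precise arms this gives the present recipe, because covariance common to all arms cancels when each contrast sums to zero. It adapts to whatever information ratio the truncated data show. With 15 mg as the Stage 2 dose the change makes the combined test stricter, so adopting it after the interim results cannot favour the drug.

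The cost is a few lines of SAS and one paragraph; no data, contrast or alpha allocation changes. SAP 5.5 Step 3 uses the same null, so a sentence there should say that Tables 15 and 16 were computed with it. No restatement of power is needed: in the simulation above, correct critical values lowered scenario 2 eGFR power from 86.2% to 85.6%.
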